## 2.4 Criteria to Prohibit the Second/Third Dose During the Study (Exit criteria):

- A diagnosis of COVID-19 with PCR test after the last dose of injection
- Severe fever (axillary temperature ≥ 38°C) for three days or allergic reaction to the previous dose of the vaccine
- SAEs following the previous shot
- Vaccination with diphtheria/tetanus vaccine between the two doses of the candidate vaccine
- Volunteer being pregnant

---

 Based on the national plan to establish and expand COVID-19 vaccination, everyone in phase 1 of vaccination priority will receive the vaccine in the next few weeks. These individuals are ineligible to participate in this study if they are in the following groups: All employees who provide first-line care to COVID-19 patients at high risk of contracting and transmitting the infection, including healthcare personnel in both the public and private sectors, the country's laboratory, faculty and staff of universities as well as the Ministry of Health, Treatment and Medical Education; People at risk of hospitalization and death due to COVID-19, including nursing home residents and nursing home staff, Veterans esp. veterans over 50% and chemical respiratory veterans living in veterans' care centers, and mentally and physically disabled people living in these centers.

A restriction applies to health workers currently in the first phase of national vaccination priorities, despite receiving general vaccinations with approved vaccines. If they wish to enroll in this trial and enter the study, there is a prohibition against it.

- A diagnosis of COVID-19 with PCR test after the last dose of injection Severe fever (axillary temperature  $\geq 38^{\circ}\text{C}$ ) for three days or severe allergic reaction (anaphylaxis) to the previous dose of the vaccine
- Receiving drugs affecting the immune system between two doses of the vaccine
- Any disease that affects a candidate's immunity level between two injections, based on the diagnosis of a medical professional

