### **2.5 Criteria for rescheduling the vaccine (after solving the problem)**

- having fever or acute illness within 7 days before or on the day of injection
- having high blood pressure (systolic pressure more than 140 or diastolic pressure more than 90 mm Hg)

**Note:** The reason/s for every volunteer's exit from the study will be recorded clearly in the eCRF while his/her safety information will be gathered till the end of the study and reflected in the final and follow-up report

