#### **4.3.1 Adverse Events (AEs)**

The AE is defined as any untoward medical events in participants that are temporally associated with the use of study interventions, whether or not considered related to vaccine/placebo. An AE can vary from clinical manifestations to abnormal test results.

After each injection, systemic and local pre-defined AEs will be registered using an online platform within three days. Solicited local AEs occur in the injection site and include pain, redness, swelling, induration, and warmth. Solicited systemic AEs are fever, chills, nausea, vomiting, malaise, fatigue, headache, diarrhea, pain in extremities, and rashes. Participants will record all these events using an online platform within three days after receiving each dose of vaccine or placebo. If any volunteer will not complete the diary, an active follow-up will be done on day four. Moreover, other unspecified symptoms (unsolicited AEs) will be followed up 28 days after each injection.

Serious Adverse Events (SAEs) are defined as any event which leads to a dangerous situation, hospitalization, longer duration of hospital stays, serious/permanent disability, congenital anomalies, requires a medical or surgical intervention to prevent permanent injury, or culminates in death. These events will be monitored up to five months after the last dosage of vaccine/placebo.

Medically Attended AEs (MAAEs) are adverse events after taking intervention that requires presentation to a health care provider, such as a general practitioner or emergency room visit for physical examinations. These events will be monitored up to five months after the last dosage of vaccine/placebo.

For monitoring and managing of AEs, the following measures will be performed:

- Active monitoring of participants for adverse events for half an hour after receiving each dose at vaccination sites.
- An Emergency medical services (EMS) ambulance will stand with three paramedics. There is an attending emergency medicine specialist with all first-aid and resuscitation equipment in place

All arrangements and coordination have been made with a supporting hospital in each city to transfer and visit participants who might suffer SAEs. In case of any SAE, the emergency specialists of the study will coordinate with the hospital an appointment for participants. We will provide 24-hour free-of-charge medical services in these hospitals for participants during the study.

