- The solicited AEs (local and systemic) are recorded in online diary forms up to 72 hours after receiving each dose by volunteers. If any volunteer does not complete the diary, an active follow-up will be done on day fourth. During this period, medical services and consultations, and hospitalization are provided to volunteers who are affected by AEs.
- Passive monitoring of unsolicited AEs from the first day until day 28th is done through spontaneous reporting by participants to call centers or go to specified hospitals.
- SAEs and MAAEs are detected passively whenever a volunteer report to the call center or consults with the hospital. These participants will be followed actively until fully recovered.
- All SAEs and MAAEs should be reported at the earliest time possible (a few days) to the sponsor and PI, who will inform DSMB to decide about unmasking and withdrawing the participants from the study.
- In case of any SAE or fatal event that needs hospitalization, the CoPIs will report the case to the Pasteur Institute of Iran via an urgent phone call, which in turn reports to FDA, and the National Ethics Committee (NEC).

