## The timetable of study activities

**Table 1. Timing of activities in Cohort 1 (2-dose scheme)**

No. of visit	1	2	3	4		
Objective of visit	Screening Dose 1, Blood sampling §	Blood sampling from a subset of subjects§	Blood sampling from a subset of subjects §	Blood sampling §	End of monitoring efficacy	End of monitoring adverse events
Month	Month 1			Month 2	Month 4	Month 6
Day	0	5	28	56		
Acceptable interval (open window period) 		+ 2	+ 7	+ 7		
Informed consent Complete eCRF (demographic info, concurrent treatments, history of underlying conditions, etc.)	•					
Blood sampling to assess the previous infection of COVID-19 (antibody assay)	•					
Physical examination 	•		•			
Randomization	•					
Intervention						
Vaccine injection and active monitoring for 0.5 hours after the shot	•		•			
Evaluation of vaccine efficacy						
Monitoring of symptomatic COVID-19 cases (ex-program visit) 	•					
Blood sampling	•			•		
Safety evaluation						
Handover of diary form to volunteers 	•		•			

Returning and reviewing of Diary form			•	•		
Recording adverse event	•					
Recording AEs which need medical intervention and those end up with study stop Recording those interventions (treatments) for AEs	•					
Recording SAEs and their related treatments	•					
Recording other treatments and vaccines during the study period 	•					

§ Among cities under the two-dose scheme (Cohort), just Sari and Babol will do serologic assays for all volunteers on days 0 and 56 and 30% of subjects on day 5 and another 30% on day 28.

1) Window period means an acceptable interval that a volunteer can come for a visit or to receive the intervention

2) A comprehensive physical examination encompasses measuring vital signs, height and weight on day 0. Before every vaccine shot, the volunteer's arm is inspected for regional lymph nodes. Every significant physical finding must be reported as a side event that needs medical intervention. Vital signs will be assessed before vaccination on days 0 and 28. Febrile subjects on day 0 (the 1st dose of vaccine) will be excluded (a temperature beyond 38°C is defined as fever). Those volunteers having fever on day 28 (the 2nd dose of vaccine) will be rescheduled for an alternative date (within the window period) to get their 2nd shot.

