All volunteers will be instructed to coordinate with the call center and go to designated laboratories for a PCR test quickly within 48 hours in case of presenting with two or more of the following symptoms lasting for over 24 hours confirmed in positive PCR testing: Fever (temperature  $\geq 38^{\circ}\text{C}$ ), chills, new cough, sore throat, nasal congestion, fatigue, muscle or body pain, headache, nausea or vomiting, diarrhea, loss of smell or taste, or at least one respiratory sign or symptom (i.e., cough, O2 saturation  $< 91$ , shortness of breath, or clinical or radiographic evidence of pneumonia).

3) Nasopharyngeal and pharyngeal swabs will be taken from the symptomatic volunteer. If the volunteer cannot be present in the lab, the operator arranges a home visit/s for him/her to take samples and clinical assessment/s. If the home visit is impossible, the symptomatic volunteer is asked to make a pharyngeal gargle with a standard method and then bring it to the lab. If PCR turns to be negative yet the symptoms last for more than 2 days, the test will be repeated after 7 days. The volunteers with positive tests who do not need hospitalization will be visited by Phone daily until full recovery of symptoms. It is important

to take note that some manifestations of COVID-19 have overlapped with systemic AEs following immunization (e.g., myalgia, headache, fever and chills). Regarding that such AEs are more common within 3 days following vaccination in case of having other symptoms of COVID-19, an infectious disease specialist judges clinically and decides whether a sample for PCR is needed. All PCR-positive cases after the 2nd shot will be counted and included to estimate vaccine efficacy (primary outcome).

4) The volunteer must record all solicited local and systemic AEs within the first 72 hours post-vaccination in their online profiles. If any volunteer did not complete the diary, an active follow-up will be done on day four. Moreover, unsolicited adverse events will be followed up 28 days after each dose, and medically attended adverse events and serious adverse events will be monitored six months after the first dose.

5) All medical treatments and other vaccines received within the 28 days after each vaccine dose as well as AEs and SAEs will be recorded. All SAEs which need medical intervention will be recorded from screening day (Day 0) till the end of follow-up (6 months after the first dose).

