**Table 2. Timing of activities in C2 (3-dose regimen)**

No. of visit	1	2	3	4		
Objective of visit	Screening Dose 1 Blood sampling from 2000 subjects of Zanjan city §	Dose 2	Dose 3	Blood sampling from 2000 subjects of Zanjan city §	End of monitoring efficacy	End of monitoring adverse events
Month	Month 1		Month 2	Month 3	Month 5	Month 7
Day	0	28	56	84		
Acceptable interval (open window period) 	0	+ 7	+ 7	+ 7		
Informed consent Complete eCRF (demographic info, concurrent treatments, history of underlying conditions, etc.)	•					
Blood sampling to assess the previous infection of COVID-19 (Antibody assay)	•					
Physical examination 	•	•	•			
Randomization	•					
Intervention						
Vaccine injection and active monitoring for 0.5 hours after the shot	•	•	•			
Evaluation of vaccine efficacy						
Monitoring of symptomatic COVID-19 (ex-program visit) 	•					
Blood sampling 	•			•		

Safety evaluation						
Handover of diary form to volunteers 	●	●	●			
Returning and review of Diary form 		●	●	●		
Recording adverse event	●					
Recording AEs which need medical intervention and those end up with study stop Recording those interventions (treatments) for AEs 	●					
Recording SAEs and their related treatments 	●					
Recording other treatments and vaccines during the study period 	●					

§ Two cities of Zanjan and Yazd follow the three-dose scheme. Just in Zanjan city, blood samples will be taken for serologic assays from 2000 volunteers on days 0 and 84.

- 1) Window period means an acceptable interval that a volunteer can come for visit or to receive the intervention
- 2) A comprehensive physical examination encompasses the measurement of vital signs, height and weight on day 0. Before every vaccine shot, the volunteer's arm is inspected for regional lymph nodes. Every significant physical finding must be reported as a side event that needs medical intervention. Vital signs will be assessed before vaccination on days 0, 28 and 56. Febrile subjects on day 0 (the 1st dose of vaccine) will be excluded (a temperature beyond 38oC is defined as fever). Those volunteers having fever on days 28 and 56 (the 2nd dose of vaccine) reschedule for an alternative date (within the window period) to get their 2nd and 3rd shots.

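### Fever that starts after the first day and outlasts the 72-hour diary cannot be checked against the three-day dose-stopping rule from the record; keep temperature entry open for these volunteers

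*Protocol*

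**What the plan says.** Section 2.4 lists, among the reasons to withhold the second or third dose, "Severe fever (axillary temperature ≥ 38°C) for three days" after the previous dose. The fever part of this criterion appears twice in the section in the same terms.

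Section 4.3.1 makes fever a solicited event and sets the recording window: "The solicited AEs (local and systemic) are recorded in online diary forms up to 72 hours after receiving each dose by volunteers". It also sets the trigger for an active contact: "If any volunteer will not complete the diary, an active follow-up will be done on day four". Table 1 note 4 and Table 2 note 5 repeat both points.

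After the diary, section 4.3.1 monitors unsolicited events passively to day 28, through reports that the volunteer makes to a call center or hospital. Follow-up to recovery is stated for two groups. For serious and medically attended events, once reported, "These participants will be followed actively until fully recovered". For PCR-confirmed cases, "The volunteers with positive tests who do not need hospitalization will be visited by Phone daily until full recovery of symptoms".

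At the next-dose visit, Table 1 schedules a physical examination and "Returning and reviewing of Diary form"; Table 2 does the same with "Returning and review of Diary form". Section 2.5 defers a dose for "having fever or acute illness within 7 days before or on the day of injection".

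**The concern.** A three-day rule is paired with a three-day diary. The record can show that the rule was met only if fever covers essentially the whole diary window. If fever begins on the second or third day and is still present at hour 72, the fact that decides the next dose lies after the record ends.

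The contact trigger does not help here. A volunteer who neglects the diary is called on day 4. A volunteer who completes it, with a last entry of 38°C or more, is not. Nothing in the protocol links a febrile last entry to any contact.

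What is at stake is participant protection. The criterion exists to keep a volunteer from another dose after a prolonged fever. If its duration has to be recalled weeks later, someone who met the criterion could be dosed again.

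**Working it through.** The protocol states no figure for this point, so there is none to reproduce. The check compares the rule, the diary and the visit schedule.

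**Inputs**
- Rule: 38°C or more for three days, taken as up to 72 hours (2.4).
- Diary: hours 0 to 72 after each dose (4.3.1; Table 1 note 4; Table 2 note 5).
- Dose 2: day 28, window +7, so days 28–35 (Tables 1 and 2).
- Dose 3 in C2: day 56, window +7, so days 56–63 (Table 2). Both windows are counted from day 0.
- Day-5 (+2) blood sampling after dose 1 in Babol and Sari: 900 volunteers (4.2 and Box 1). The Table 1 footnote gives 30%, which is 0.30 × 6,000 = 1,800 if taken over both cities.
- Sample sizes: C1 14,400 vaccine and 3,600 placebo; C2 4,800 vaccine and 1,200 placebo (6.1).

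**1. What the diary can show.** Fever on each of the three diary days meets the rule from the record. Fever starting at hour 24 and present at hour 72 has 72 − 24 = 48 hours on record, so its third day is unrecorded. The latest relevant onset, hour 72, completes three days at 72 + 72 = 144 hours, which is day 6.

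**2. Gap from diary close to the next-dose visit.**
- Dose 1 to dose 2: the diary closes on day 3. The gap is 28 − 3 = 25 to 35 − 3 = 32 days.
- C2 dose 2 to dose 3: the diary closes on days 31–38. The gap is 56 − 38 = 18 to 63 − 31 = 32 days. With dose 2 given exactly on day 28, it is 56 − 31 = 25 to 63 − 31 = 32 days.

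**3. Who has a visit in between.** After dose 1, 900/24,000 = 3.75% or 1,800/24,000 = 7.5%. That leaves 96.25% or 92.5% with none. Nobody has an interim visit between doses 2 and 3 in C2. Table 1 lists blood sampling at the day-5 visit, with no physical examination or diary review.

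**4. Whether section 2.5 catches it.** The shortest dose interval is 28 days (dose 1 to 2) or 56 − 35 = 21 days (C2 dose 2 to 3). The seven-day look-back therefore starts no earlier than day 28 − 7 = 21 or day 21 − 7 = 14 after the previous dose. The fever in question completes its three days by day 6, at least 14 − 6 = 8 days before the look-back opens. Section 2.5 would not ask about it.

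**5. Reach of a day-4 call alone.** Contact at about 96 hours confirms three days only for onset by 96 − 72 = 24 hours. Later onset needs recording beyond day 4.

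**6. Doses to which the rule applies.** First doses 18,000 + 6,000, plus C2 second doses 6,000, give 30,000. Of these, 14,400 + 4,800 + 4,800 = 24,000 are vaccine and 3,600 + 1,200 + 1,200 = 6,000 placebo, ignoring dropout. This is a denominator only. The protocol gives no rate of fever at 72 hours, so the number affected cannot be derived.

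**The case against.** **The record often suffices.** A reader might infer that the whole three-day rule rests on recall. The protocol does not support that: fever on all three diary days is documented when it happens. Only later-onset fever that passes hour 72 is affected.

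**Some volunteers are seen.** A reader might also infer that no volunteer has a scheduled contact before the next dose. The day-5 (+2) subset in Babol and Sari attends on days 5–7, close to the day that matters. This is a small share, after dose 1 only, and no fever review is listed.

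**There is an instructed route.** The Table 1 notes tell volunteers with two or more listed symptoms for over 24 hours to contact the call center and be tested within 48 hours. Fever, chills, headache, fatigue and muscle pain are all on the list. In both cohorts a negative test is repeated after 7 days if symptoms last more than 2 days. Adverse events can also be reported by telephone or in person (6.5). These routes will catch many prolonged fevers. They still depend on the volunteer. Fever alone does not reach two symptoms, and no temperature log is specified along the way. In the first days after a dose, an infectious disease specialist may also judge that no PCR sample is needed.

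**Staff can ask at the next-dose visit.** Diary review puts the hour-72 fever in front of them. Other criteria in 2.4, such as interim drugs or a tetanus vaccination, are likewise settled without an interim contact. That is ordinary practice and a fair point. The difference is that fever duration is a measurement, harder to recall weeks later than whether a drug or vaccine was received, and the tool to record it is already in use.

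Together these arguments narrow the gap considerably. They do not close it.

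**Conclusion.** The point holds in a limited form. For fever that starts after the first day and is still present at hour 72, the protocol fixes a dose-stopping rule that its own recording schedule cannot confirm. For most volunteers, duration would be settled 18 to 32 days after the diary closes, from recall or from an earlier report that the volunteer started.

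The number affected is unknown and probably small. The 30,000 doses are those to which the rule applies and must not be read as volunteers at risk. A reader might infer bias in the efficacy or adverse-event results. The protocol gives no ground for that: the gap concerns a dosing decision for a few individuals, and no planned analysis is biased by it.

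This is an inexpensive improvement to participant safety. It rests on two assumptions: that three days means up to 72 hours, and that dose windows run from day 0. If dose 3 were instead timed from the actual dose 2, the C2 gap would be 25 to 32 days and the conclusion would be the same.

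**What to change.** Leave the criterion in 2.4 as it is. In 4.3.1, Table 1 note 4 and Table 2 note 5:
- Keep the online temperature entry open for any volunteer whose last diary entry is 38°C or more, until the fever resolves or three days are reached, which is day 6 after the dose at the latest. This is the main remedy, because a day-4 call alone reaches only about 96 hours.
- Extend the existing day-4 contact to these volunteers through an automatic flag in the online diary, so that nobody has to screen completed diaries by hand.

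The cost is one platform flag with a conditional entry field open for at most three extra days, slightly more diary burden, and a few more calls by the existing day-4 team, for febrile volunteers only. Fever that first appears after hour 72 stays on the passive reporting route.

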### **2.5 Criteria for rescheduling the vaccine (after solving the problem)**

- having fever or acute illness within 7 days before or on the day of injection
- having high blood pressure (systolic pressure more than 140 or diastolic pressure more than 90 mm Hg)

**Note:** The reason/s for every volunteer's exit from the study will be recorded clearly in the eCRF while his/her safety information will be gathered till the end of the study and reflected in the final and follow-up report

### **2.6 Criteria to hold the study**

- Recognition of executive or planning issues in the study, which need investigation
- Detection of potential safety issues for participants by DSMB
- Safety issues diagnosed by the sponsor based on the DSMB report or independently
- Suspected Unexpected Serious Adverse Reactions (SUSAR): If a SUSAR occurs, the study stops temporarily as of investigation team concludes the causality of SAR and decides to stop or continue the study
- A request be sent by the National Committee for Ethics in Biomedical Research to hold the study
- A request be sent by the NRA (national regulatory authority, FDA) to hold the study

## **3. Interventions**

The participants will receive the vaccine candidates according to two schemes (cohorts).

## **C1: Two-dose Scheme**

Intervention group: Intramuscular injection (Deltoid muscle) of 25 µg SOBERANA-02 vaccine on days 0 and 28

Placebo group: Intramuscular injection of placebo on days 0 and 28

## **C2: Three-dose Scheme**

Intervention group: Intramuscular injection (Deltoid muscle) of 25 µg SOBERANA-02 vaccine on days 0 and 28 as well as a third dose with SOBERANA-plus on day 56

Placebo group: Intramuscular injection of placebo on days 0, 28 and 56

### **3.1 Patient Recruitment**

**3.1.1 First stage:** We will invite the public via social networks, text messages, and media. Our trained staff will define the objectives of the study and inclusion criteria for participants and make sure that everyone understands them. Further information will be available on the recruiting website. Participants can register on the website after assessing the eligibility criteria. The required registration items will be the city name, national ID number, phone number, and history of underlying disease(s). Healthy people with chronic conditions that are under control (diabetes, liver or renal disease, and hypertension) can participate in the study after a complete examination by the study physician and laboratory results in the following range:

- Chronic renal disease (GFR > 30 CC/min calculated based on the blood creatinine level)
- Chronic liver disease (AST < 100 U/L, ALT < 150 U/L)
- Type 2 diabetes mellitus (HbA1C < 7.5%)
- Hypertension (Systolic blood pressure < 140 mmHg and diastolic blood pressure < 90 mmHg on medication based on self-declaration and on-site vital sign assessment)

**3.1.2 Second stage:** The eligible volunteers will receive preliminary approval by a text message containing the appointment date, time, and address of the vaccination

**3.1.3 Third stage (visit 1):** In case of any ambiguity about the situation, volunteers can ask further questions from research physicians.

After taking the informed consent in two copies, the physician will examine the volunteers and order further screening or laboratory analyses. All consenting participants will be screened for underlying chronic conditions and COVID-19-related clinical symptoms. Then volunteers will receive a unique randomization ID that helps them to check their vaccination status until the end of the study.

